7.1.3 Analysis of Covariance (ANCOVA)

In summaries of efficacy endpoints examining changes from baseline at Week 52 in the short-term analysis, and week 156 in the short-term and long-term analysis, ANCOVA of the differences between post-baseline and baseline measurements will be performed, with treatment group as an effect and the baseline measurement as a covariate.

The following ANCOVA model will be used:

$$D_{t,ij} = \text{intercept} + \beta [Y_{0,ij}] + \tau_i + \text{error}_{ij}$$

(Model 7.1.3.1)

where:

$D_{t,ij} = Y_{24,ij} - Y_{0,ij}$ = the Week 52 change from baseline of subject j in treatment group i (as defined in Section 7.1.1.2 and Section 8 on conventions),

$Y_{0,ij}$ is the baseline measurement of subject j in treatment group i ,

$Y_{24,ij}$ is the Week 52 measurement of subject j in treatment group i ,

β is the slope of $D_{t,ij}$ regressing on the baseline measurement and,

τ_i is the mean effect of treatment group i .

Intercept, β , and τ_i are unknown parameters to be estimated from the data.

The model will provide least squares mean estimates and 2-sided 95% confidence intervals for mean changes from baseline within and (when warranted) differences in mean change from baseline between treatments. Where applicable, t-statistics corresponding to the Type III sums of squares for the differences in the least squares means will be used to obtain p-values for treatment group comparisons.

Model assumptions will be checked.

7.1.4 Descriptive Summaries of Continuous Variables

Descriptive summaries of continuous variables in terms of change or percent change from baseline values will be provided, including n, mean, median, first quartile (Q1) and third quartile (Q3) and standard error (SE). Geometric mean and coefficient of variation (CV) will be also be provided for lipid panel results. In addition, 95% confidence interval for the mean (percent) change from baseline will be calculated for continuous efficacy variables. They will be presented by treatment group and time point where applicable.

7.1.5 Descriptive Summaries of Categorical Variables

Descriptive summaries of categorical variables will consist of frequencies and percentages for each treatment group and overall, where applicable.

7.1.6 Descriptive Summaries of Change from Baseline in Categorical Variables

Descriptive summaries of change from baseline in categorical variables will be provided using shift tables. Frequencies and percentages of subjects within each treatment group will be generated for levels of cross-classifications of baseline and the on-treatment value of the parameter. The on-treatment value can either be the value at a certain time point, or e.g., for laboratory tests, the minimum/maximum value in the direction of toxicity, which has been observed during the short-term double-blind treatment period, or during the short-term and long-term treatment period. Treatment group differences will not be assessed in summaries of shifts.

7.1.7 Kaplan-Meier Curve and Estimates for Time-to-Event Analyses

Kaplan-Meier plots² of time to event variables will be displayed by treatment group. Additionally, a table will accompany the plot and will display the Kaplan-Meier estimates of the cumulative proportion (with 95% CI calculated based on Greenwood's method³ when applicable) of subjects with event at specific time points by treatment group. If the estimated lower bound of 95% CI is below 0 or the estimated upper bound of 95% CI is over 1, then it will be restricted to 0 or 1, respectively.

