3.5.2 Rescue Guidelines for Subjects with Protocol-Defined Lack of Glycemic Control

During the course of the trial, subjects may be eligible for the addition of open-label rescue medication to their blinded treatment regimen in order to treat ongoing hyperglycemia. Insulin is recommended as the first-line rescue therapy, as subjects will already be taking dual or triple-therapy (based on their randomization assignment). If a subject refuses treatment with insulin or is not a candidate for insulin, other options for rescue therapy can be considered. However, initiation of a DPP4 inhibitor, SGLT2 inhibitor, or SU is not permitted for rescue therapy. The sub-sections and tables listed below define the lack of glycemic control criteria for initiation of rescue medication in both short-term and long-term periods of the study.

Pre-specified glycemic criteria (see Table 3.5.2-1), based upon central laboratory HbA1c, FPG, and repeat confirmatory FPG were established during the treatment period; to determine eligibility for open-label rescue medication, FPG is to be used from Week 9 to Week 52, and HbA1c after Week 52 to Week 156.

Table 3.5.2-1: Lack of Glycemic Control Criteria for Initiation of Rescue Medication

Visit Label	Central Laboratory FPG/HbA1c
Week 9	FPG > 270 mg/dL (15.0 mmol/L)
After Week 9 to Week 16 (including Week 16)	FPG > 240 mg/dL (13.3 mmol/L)
After Week 16 to Week 28 (including Week 28)	FPG > 220 mg/dL (12.2 mmol/L)
After Week 28 to Week 52 (including Week 52)	FPG > 200 mg/dL (11.1 mmol/L)
After Week 52 to Week 156	HbA1c > 7.5%

Subjects with a central laboratory FPG value meeting the lack of glycemic control criterion at a pre-specified visit will be scheduled for a follow-up visit (within 3 - 5 days) to obtain a second central laboratory FPG value and review the subject's glucose meter readings.

If the repeat central laboratory FPG value still meets the criterion, the subject must be rescued. Subjects who meet rescue criteria in the blinded treatment period must first complete the Rescue Visit procedures before receiving open-label rescue medication to ensure that important trial endpoint measurements are collected.

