7.5.4 Secondary Efficacy Analyses

In order to protect the overall type I error rate, the interpretation of the statistical significance of treatment comparisons for each secondary efficacy endpoint will be done using a step-wise procedure as outlined in Section 7.5.1

The ordered list of secondary endpoints for the sequential testing procedure is:

- Mean change from baseline in total body weight at Week 52.
- Percent of subjects achieving a therapeutic glycemic response, defined as HbA1c < 7.0%, at Week 52.
- Mean change from baseline in SBP at Week 52.

- Time to treatment intensification (addition of insulin or other glucose-lowering agent for rescue therapy or discontinuation for lack of glycemic control) during the 52-week double-blind treatment period.
- Time to treatment intensification (addition of insulin or other glucose-lowering agent for rescue therapy or discontinuation for lack of glycemic control) during the 156-week treatment period.
- Proportion of subjects achieving a therapeutic glycemic response, defined as HbA1c < 7.0%, at Week 156

The analysis of change from baseline for total body weight and SBP will be performed using the same longitudinal repeated measures model as for the primary efficacy endpoint.

The proportion of subjects achieving a therapeutic glycemic response (defined as HbA1c < 7.0%) at Week 52 and Week 156 will be summarized by treatment group and compared between treatment groups using logistic regression, adjusting for baseline Hb1Ac. The 95% confidence intervals for the response rate within each treatment group, as well as for the difference in response rates between treatment groups, will be calculated with adjustment for baseline HbA1c. Subjects who are rescued, discontinued or have missed measurements at Week t (t = 52 and 156, respectively) will be considered as not achieving glycemic response.

Time to treatment intensification will be analyzed using a Cox proportional hazards model. Estimates of the hazard ratio and 95% confidence intervals will be provided. This analysis will be performed only when there are at least 10 events in each treatment group. Kaplan-Meier estimates will be calculated and plotted by treatment group. For the analysis during 52 / 156 weeks, all subjects will be censored at 52 / 156 week short-term / long-term treatment period if treatment intensification has not occurred by then. Subjects rescued at Week 52 / 156 visit will be counted as having an event for the analysis.

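### The clipped Greenwood limits in the Kaplan-Meier table cover below 95%, and sit too low, where an arm has few events; the limits are descriptive, so the point is minor

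*SAP*

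**What the plan says.** SAP 7.1.7 provides a table beside each Kaplan-Meier plot. It shows the cumulative proportion "of subjects with event at specific time points by treatment group", "with 95% CI calculated based on Greenwood's method", with a qualifier that the interval is given when it applies. The next sentence sets the truncation rule. It begins "If the estimated lower bound of 95% CI is below 0 or the estimated upper bound of 95% CI is over 1" and ends "then it will be restricted to 0 or 1, respectively". No transformation is mentioned.

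The method serves time to treatment intensification over 52 and 156 weeks (SAP 7.5.4). For the Cox model, SAP 7.5.4 says "This analysis will be performed only when there are at least 10 events in each treatment group". For the curve it says only that "Kaplan-Meier estimates will be calculated and plotted by treatment group", with no minimum number of events. Subjects without an event are handled by administrative censoring: "all subjects will be censored at 52 / 156 week short-term / long-term treatment period".

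The glycaemic rescue criteria that generate most events begin at Week 9. Protocol 3.5.2 states that "FPG is to be used from Week 9 to Week 52", with HbA1c used after that. SAP 7.1.8 has a small-count rule for response proportions (an exact interval when any arm has fewer than 5 responders). SAP 7.1.7 has no equivalent.

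**The concern.** A log(-log) or logit interval cannot leave the range 0 to 1, so it needs no clipping. A rule that clips both ends therefore points to estimate ± 1.96 × SE on the probability scale. At small proportions the sampling distribution is skewed, and the standard error shrinks along with the estimate. When the observed count happens to be low, the interval is both too low and too short, and it misses the true value from below. Clipping does not cause this; it is a symptom of the linear scale.

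At stake is the accuracy of the printed error bars. In a sparse arm, or early on the curve, the table would understate how high the proportion needing intensification could plausibly be.

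**Working it through.** **Plan's own figure.** The only computed design figure is the primary sample size (SAP 5): difference 0.35%, SD 1.1%, two-sided 0.05, 90% power, 5% non-evaluable.

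n per arm = 2 × (1.960 + 1.2816)² × 1.1² / 0.35² = 207.6, so 208. Then 208 / 0.95 = 218.9, so 219, against 220 stated. It reproduces, and it fixes the arm size for this check.

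**Inputs.** n = 220 per arm: efficacy uses the Randomized Subjects Data Set, and event-free subjects are censored, not dropped. The true event proportion is an assumption, scanned because the documents give none. The Cox threshold of 10 events corresponds to 10/220 = 4.5%.

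**Interval.** Without interim censoring, Kaplan-Meier with Greenwood variance reduces to p ± 1.96 × √(p(1 − p)/n), clipped to 0 and 1.

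- 3/220: p = 1.364%, SE = 0.782%. The lower limit is −0.17%, clipped to 0; the upper limit is 2.90%.
- 4/220: p = 1.818%, SE = 0.901%. The lower limit is +0.05%, so clipping at 0 acts only at 3 events or fewer.
- 0/220: SE = 0. The interval is 0 to 0, or is not shown if the qualifier in SAP 7.1.7 is read that way. The exact upper limit is 1 − 0.025^(1/220) = 1.66%.

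**Coverage.** For each true proportion, sum the binomial probabilities of the counts whose interval contains it. Example at 1.5%: counts 0 and 1 give upper limits of 0 and 1.34%, both below 1.5%. Their probability is 3.597% + 12.052% = 15.649%. Another 0.2% of intervals lie wholly above the truth, so coverage is 84.2%.

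| True proportion | Coverage, clipped linear | Interval wholly too low | Interval wholly too high |
|---|---|---|---|
| 0.5% | 66.7% | 33.2% | 0.1% |
| 1% | 88.9% | 11.0% | 0.2% |
| 1.5% | 84.2% | 15.6% | 0.2% |
| 2% | 93.0% | 6.4% | 0.5% |
| 3% | 89.1% | 10.2% | 0.7% |
| 4.5% | 92.2% | 6.7% | 1.1% |
| 10% | 94.8% | 4.0% | 1.2% |
| 20% | 94.5% | 3.5% | 2.0% |

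Coverage oscillates between neighbouring proportions, so averages are the fairer summary. The alternative in the last two columns is log(-log) limits with the exact upper limit at zero events.

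| Expected events | Clipped linear, mean | Clipped linear, minimum | Alternative, mean | Alternative, minimum |
|---|---|---|---|---|
| 1–5 | 86.1% | 63.2% | 96.0% | 93.1% |
| 5–10 | 91.9% | 87.3% | 96.1% | 94.7% |
| 1–10 | 89.3% | 63.2% | 96.0% | 93.2% |
| 10–20 | 93.6% | 90.3% | 95.4% | 94.1% |
| 20–44 | 94.3% | 92.6% | 95.2% | 93.9% |

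Over 1–10 expected events, 10.1% of the clipped linear intervals lie wholly below the truth, against a nominal 2.5%.

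**Interim censoring.** In simulation (10,000 trials per setting, exponential event times) with 30% censored by the time point, coverage was 84.9% at 1%, 88.5% at 2%, 91.0% at 3% and 92.7% at 4.5%. The pattern is the same.

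**Alternative, worked for 3/220.** S = 1 − 3/220; log(−log S) = −4.288; SE on that scale = √(3/(220 × 217)) / |log S| = 0.577. Limits −4.288 ± 1.96 × 0.577 = −5.420 and −3.157 convert back to 0.44% and 4.17% (exact binomial: 0.28% to 3.93%). Log(-log) alone is not enough: it also collapses to 0 to 0 with no events and averages only 73.2% over 1–2 expected events. The exact limit at zero is needed.

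**The case against.** The strongest reply is that linear Greenwood limits are a recognised method, that these are single-arm descriptive limits, and that they feed no decision. The tested quantity is the Cox hazard ratio. This stands, and it sets the severity.

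Four stronger readings are tempting, and the documents do not support them.

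- **The plan expects sparse data because it clips at 0.** The rule is generic and clips at 1 as well, and no event rate is given. After Week 52 the rescue trigger becomes HbA1c above 7.5% in subjects enrolled at 7.5% to 10.5%, so Week 156 may well lie outside the sparse range. What holds is that the plan permits sparse estimates and that early time points are likely to be sparse.
- **These intervals become the inference for a hierarchy endpoint when the Cox model is dropped.** They would be the only stated uncertainty, but within-arm limits do not test a difference. The missing between-arm analysis is a separate matter that this change leaves untouched.
- **With no events the plan prints 0 to 0.** That is one reading. The qualifier also allows no interval to be shown.
- **The shortfall is larger, using 209 per arm.** The 5% allowance belongs to the HbA1c sample-size calculation. At 209, coverage at 1.5% would be 81.8%, but about 220 is the right denominator.

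It is also fair that the linear scale is inferred, not stated. The other reading that could need clipping, a log-survival interval, gives almost the same coverage (89.1% at 3%), so the result does not depend on it.

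**Conclusion.** The point holds as a minor one. Read as linear-scale limits, the intervals in SAP 7.1.7 fall clearly short of 95% below about 5 expected events per arm (average 86%), moderately short at 5 to 10 (92%), and only slightly short at 20 to 44 (94%). The error is one-directional: nearly all misses understate the event proportion.

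This rests on the inferred linear scale, about 220 subjects per arm, no interim censoring for the exact figures, and assumed event proportions. Whether the Week 52 or Week 156 estimate falls in the affected range cannot be known from the documents. The primary result, type I error and the testing hierarchy are unaffected.

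**What to change.** In SAP 7.1.7, specify log(-log)-transformed Greenwood limits, give the exact binomial upper limit among those still at risk where no event has occurred, and delete the truncation sentence.

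The cost is one sentence and a standard software option; no data or tests change. Upper limits widen at very small counts (1/220: from 1.3% to 3.2%; 9/220: from 6.7% to 7.7%). The tails are not perfectly balanced: at a true proportion of 1.5%, 5.0% of the new intervals lie wholly above the truth, and the average over 1–10 expected events is 3.4% against a nominal 2.5%.

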7.1.8 Proportion of Subjects Achieving Pre-defined Characteristic

Unless otherwise specified, the proportion of subjects with a pre-defined characteristic at Week t will be analyzed using logistic regression with adjustment for baseline HbA1c value. Subjects in the randomized treatment group who do not demonstrate achieving therapeutic glycemic response at a specified timepoint or are rescued will count as treatment failures from that timepoint. When proportion of responders (e.g., meeting HbA1c criteria) is needed, the estimates, confidence intervals, and tests will be obtained using this methodology with adjustment for baseline variable (e.g., adjustment for baseline HbA1c). For each treatment group, the probability of response is first modeled using a logistic regression model with baseline (e.g., baseline HbA1c) as a covariate.

When there are less than 5 responders in any treatment group, the unadjusted (and difference in) proportions, exact 95% confidence interval, and p-values from the Fisher's exact test (when applicable) will be provided.

For composite response endpoints (glycemic control without hypoglycemia or weight gain), the proportion of subjects achieving targets will be summarized by treatment group without adjustment for baseline.

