8.4.2.3 Other Efficacy Analyses

Analyses for other efficacy objectives will use the same methodology for continuous endpoints as described above. For composite response endpoints (glycemic control without hypoglycemia or weight gain), the proportion of subjects achieving targets will be summarized by treatment group without adjustment for baseline. All exploratory endpoints will not be statistically tested.

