3.3 Exploratory Objectives

Short-term:

- To assess the proportion of subjects achieving therapeutic glycemic response, defined as HbA1c < 7.0%, without any hypoglycemia at Week 52 achieved with saxagliptin, in co-administration with dapagliflozin, added to current background therapy with metformin, compared to glimepiride added to current background therapy with metformin.
- To assess the proportion of subjects achieving therapeutic glycemic response, defined as HbA1c < 7.0%, without any hypoglycemia and weight gain at Week 52 achieved with saxagliptin, in co-administration with dapagliflozin, added to current background therapy with metformin, compared to glimepiride added to current background therapy with metformin.
- To assess mean change from baseline in fasting plasma glucose (FPG) achieved with saxagliptin, in co-administration with dapagliflozin, added to current background therapy with metformin, compared to glimepiride added to current background therapy with metformin at Week 52.
- To assess change from baseline of metabolic measures (glucagon, C-peptide, pro-insulin, insulin, iHOMA2) at Week 52 achieved with saxagliptin, in co-administration with dapagliflozin, added to current background therapy with metformin, compared to glimepiride added to current background therapy with metformin.
- To assess change from baseline in average glucose values and post-prandial glucose values measured by 6-point self-monitored blood glucose (SMBG) profiles at Week 52 achieved with saxagliptin, in co-administration with dapagliflozin, added to current background therapy with metformin, compared to glimepiride added to current background therapy with metformin.
- To assess change from baseline of urinary albumin to creatinine ratio at Week 52 achieved with saxagliptin, in co-administration with dapagliflozin, added to current background therapy with metformin, compared to glimepiride added to current background therapy with metformin.
- To assess change from baseline of biomarkers (high-sensitivity C-reactive protein [hsCRP], N-terminal pro-brain natriuretic peptide [NT Pro-BNP]) at Week 52 of double-blind treatment achieved with saxagliptin, in co-administration with dapagliflozin, added to current background therapy with metformin, compared to glimepiride added to current background therapy with metformin.

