4.3 Exploratory Endpoints

The exploratory endpoints for the short-term treatment period include:

- Proportion of subjects achieving a therapeutic glycemic response, defined as HbA1c < 7.0%, without any hypoglycemia at Week 52.
- Proportion of subjects achieving a therapeutic glycemic response, defined as HbA1c < 7.0%, without any hypoglycemia and weight gain at Week 52.
- Mean change from baseline in FPG at Week 52.
- Mean change from baseline of metabolic measures (glucagon, C-peptide, pro-insulin, insulin, iHOMA2) at Week 52.
- Mean change from baseline in average glucose values and post-prandial glucose values measured by 6-point SMBG profiles at Week 52.
- Mean change from baseline in urinary albumin to creatinine ratio at Week 52.
- Mean change from baseline in biomarkers (hsCRP and NT Pro-BNP) at Week 52.
- Mean change from baseline in patient-reported treatment satisfaction, quality of life, and barriers to medication adherence at Week 52.
- In a sub-study: Mean change from baseline in glucose variability, as defined by mean amplitude of glycemic excursions (MAGE), using CGM at Week 52.
- In a sub-study:
 - Mean change from baseline in visceral and subcutaneous adipose tissue volume as assessed by MRI at Week 52 in the subpopulation of subjects who undergo MRI-PDFF.
 - Mean change from baseline in percent hepatic lipid content as assessed by MRI at Week 52 in the subpopulation of subjects who undergo MRI-PDFF.

The exploratory endpoints for the long-term treatment period include:

- Mean change from baseline in HbA1c at Week 156.
- Mean time spent at or below HbA1c target (HbA1c < 7.0%) during 156 weeks.
- Proportion of subjects achieving a therapeutic glycemic response, defined as HbA1c < 7.0%, without any hypoglycemia at Week 156.
- Proportion of subjects achieving a therapeutic glycemic response, defined as HbA1c < 7.0%, without any hypoglycemia and weight gain at Week 156.
- Mean change from baseline in FPG at Week 156.
- Mean change from baseline of metabolic measures (glucagon, C-peptide, pro-insulin, insulin, iHOMA2) at Week 156.
- Mean change from baseline in urinary albumin to creatinine ratio at Week 156.
- Mean change from baseline in biomarkers (hsCRP and NT Pro-BNP) at Week 156.

- Mean change from baseline in total body weight at Week 156.
- Mean change from baseline in SBP at Week 156.
- Mean change from baseline in patient-reported treatment satisfaction, quality of life, and barriers to medication adherence at Week 156.

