7.5.5 Exploratory Efficacy Analyses

No adjustments for multiplicity will be done for exploratory endpoints; only nominal p-values will be presented.

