7.5.5.1 Proportion of Subjects Achieving Composite Response Targets

The proportion of subjects achieving composite response targets will be summarized by treatment group without adjustment for baseline for the following composite response endpoints:

- Proportion of subjects achieving a therapeutic glycemic response, defined as HbA1c < 7.0%, without any hypoglycemia at Week 52.
- Proportion of subjects achieving a therapeutic glycemic response, defined as HbA1c < 7.0%, without any hypoglycemia and weight gain at Week 52.
- Proportion of subjects achieving a therapeutic glycemic response, defined as HbA1c < 7.0%, without any hypoglycemia at Week 156.
- Proportion of subjects achieving a therapeutic glycemic response, defined as HbA1c < 7.0%, without any hypoglycemia and weight gain at Week 156.

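### The exploratory composite responder endpoints are framed against glimepiride but reported only as raw proportions by arm, with no between-arm estimate, interval or baseline adjustment

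*SAP*

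**What the plan says.** SAP 3.3 gives the first composite objective as "To assess the proportion of subjects achieving therapeutic glycemic response, defined as HbA1c < 7.0%, without any hypoglycemia at Week 52", and the sentence goes on to name glimepiride plus metformin as the comparator. The other three composite objectives, and their counterparts in Protocol 1.3.3, have the same form.

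The analysis is descriptive in all three places that cover it:

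- Protocol 8.4.2.3, on the composites: "the proportion of subjects achieving targets will be summarized by treatment group without adjustment for baseline".
- SAP 7.1.8: the composites are "summarized by treatment group without adjustment for baseline".
- SAP 7.5.5.1: "The proportion of subjects achieving composite response targets will be summarized by treatment group without adjustment for baseline", followed by the four endpoints.

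The default in SAP 7.1.8 for responder proportions is logistic regression adjusted for baseline HbA1c, unless another method is specified. HbA1c below 7.0% on its own follows that default. It is a secondary endpoint in the testing sequence, and SAP 7.5.4 gives it an adjusted between-arm difference with an interval. SAP 7.1.8 also has a fallback for fewer than 5 responders in an arm (unadjusted difference, exact interval, Fisher's test), but does not say whether it covers the composites.

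On testing, Protocol 8.4.2.3 states "All exploratory endpoints will not be statistically tested", while SAP 7.5.5 states "No adjustments for multiplicity will be done for exploratory endpoints; only nominal p-values will be presented". SAP 7.5.5.1 names no test for the composites.

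**The concern.** The objective asks how the combination does relative to glimepiride, but the analysis stops at one percentage per arm. Readers will subtract the two figures themselves, without an interval. Most other exploratory efficacy endpoints get a model-based comparison (SAP 7.5.5.2, 7.5.5.4 and 7.5.9). Lipids and biomarkers are the main ones left descriptive (SAP 7.5.5.3 and 7.5.8).

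The composites are also close to the trial's rationale. Both introductions describe the ideal add-on as one that lowers HbA1c strongly, with weight loss and no hypoglycemia.

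Every composite requires HbA1c below 7.0%, and Protocol 3.3.1 admits subjects from 7.5% to 10.5%, so baseline HbA1c should predict response. Leaving it out costs some precision and leaves the visible difference exposed to chance imbalance in baseline. At stake is how four exploratory results can be read. The primary and secondary conclusions are not affected.

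**Working it through.** **The plan's own figure.** No response rate or precision is stated for the composites. The only sample-size statement (Protocol 8.1, SAP 5) is for the primary endpoint, and it reproduces: with difference 0.35, SD 1.1, two-sided alpha 0.05 and 90% power, n = 2(1.960 + 1.282)² × 1.1² / 0.35² gives 208 evaluable per arm, and 208 / 0.95 gives 219, against 220 stated. Nothing below alters it.

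**Uncertainty that goes unreported.** For an unadjusted difference with 220 per arm, the 95% half-width is 1.96 × √[p₁(1−p₁)/220 + p₂(1−p₂)/220]. The rates are assumptions.

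- 20% v 10%: 1.96 × √[(0.16 + 0.09)/220] = 6.6 points
- 30% v 20%: 1.96 × √[(0.21 + 0.16)/220] = 8.0 points
- 45% v 35%: 1.96 × √[(0.2475 + 0.2275)/220] = 9.1 points

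**Gain from adjustment.** The documents do not give the strength of the association between baseline HbA1c and composite response, so it was varied as an odds ratio per SD of baseline from 1.0 (none) to 0.4. Each scenario used 3,000 simulated trials of 220 per arm with normally distributed baseline. The raw difference p̂₁ − p̂₂ was compared with the standardised difference, which is the average over all subjects of expit(a + b + c·xᵢ) − expit(a + c·xᵢ), from a logistic model with intercept a, treatment effect b and baseline slope c.

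Variance ratio, adjusted / raw:

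| Odds ratio per SD | 20% v 10% | 30% v 20% | 40% v 25% |
|---|---|---|---|
| 1.0 | 1.003 | 1.001 | 1.001 |
| 0.7 | 0.995 | 0.984 | 0.967 |
| 0.5 | 0.947 | 0.920 | 0.909 |
| 0.4 | 0.920 | 0.860 | 0.877 |

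The largest reduction is 1 − 0.860 = 14%. The standard error ratio is then √0.860 = 0.927, about 7% smaller. In that scenario the power of a nominal test goes from 68.4% to 74.7%. The mean raw and adjusted estimates agree to within 0.04 points in every scenario, so neither is biased relative to the other.

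**Chance imbalance.** The standard error of the between-arm difference in standardised baseline is √(2/220) = 0.095 SD, and 1.96 of these is 0.187 SD. The raw difference shifts with such an imbalance by (percentage points, absolute value):

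| Odds ratio per SD | 20% v 10% | 30% v 20% | 40% v 25% |
|---|---|---|---|
| 1.0 | 0.06 | 0.14 | 0.17 |
| 0.7 | 0.65 | 1.11 | 1.62 |
| 0.5 | 1.43 | 2.35 | 2.60 |
| 0.4 | 1.79 | 2.98 | 3.02 |

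The first row is simulation noise around zero. Under simple randomisation an imbalance this large in either direction arises in about 5% of trials.

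**Weight composites.** A smaller and therefore noisier simulation (500 trials per scenario) assumed 15% missing counted as non-response and no weight gain in 80% v 40%. The variance reduction was about 0 to 6%. The added component dilutes the link with baseline HbA1c.

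**The case against.** The strongest reply is that the plan does what it set out to do. Protocol 8.4.2.3 and SAP 7.1.8 and 7.5.5.1 give the same rule, and the default in 7.1.8 allows for exceptions. The protocol's statement that exploratory endpoints are not tested explains why a summary was thought enough. All of that stands. A reader might infer that the documents contradict themselves because HbA1c below 7.0% is adjusted and the composites are not. They do not: one is a tested secondary endpoint and the others are listed as exploratory in Protocol 8.3.3 and SAP 4.3.

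A reader might also infer that the raw comparison is biased. It is not. Randomisation makes the raw proportions unbiased, and adjustment addresses only precision and chance imbalance in the trial at hand. The treatment-assignment text is redacted (Protocol 4.4, SAP 2.2), so any stratification factors cannot be seen. If baseline HbA1c was one of them, the imbalance argument largely falls away.

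A larger gain, up to about 20%, can be obtained by assuming baseline HbA1c N(8.5, 0.8), a slope of change on baseline of −0.3 to −0.5, residual SD 0.7 to 0.85 and no missing data. Those inputs do not fit the plan well. They put half the subjects at or below 8.5%, where Protocol 3.3.1 caps the 7.5–8.5% group at 40%. They imply an SD of change of at most √(0.85² + (0.5 × 0.8)²) = 0.94, against 1.1 in the sample-size section. They also omit the weight component and the counting of missing values as non-response.

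What the reply does not answer is that the objective names a comparator while no between-arm estimate is specified, and that the two documents differ on p-values.

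**Conclusion.** A minor but real gap in reporting. The four composites have comparative objectives and a purely descriptive analysis, so no effect size or interval is planned, although an unadjusted difference would carry a half-width of roughly 6.6 to 9.1 points. Adjustment for baseline HbA1c would add a modest amount: 0 to about 14% less variance, and protection against a shift of 0 to about 3 points at a 1.96-standard-error imbalance. These ranges rest on assumed response rates and associations. The zero end requires that baseline HbA1c does not predict the composite, which is unlikely for an endpoint that demands HbA1c below 7.0%. The missing interval is the larger part of the point, and adjustment is the secondary gain.

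It would go too far to conclude that any error rate, power statement or confirmatory result is affected. The composites lie outside the testing sequence.

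**What to change.** 1. In SAP 7.1.8 and 7.5.5.1 and Protocol 8.4.2.3, keep the raw proportions and add a between-arm risk difference standardised from the logistic model with treatment and baseline HbA1c, with a 95% confidence interval. An odds ratio is optional; the variance gain above refers to the risk difference. Label the result exploratory and make no significance claim. The current 7.1.8 does not describe the standardisation step, so write it out.
2. State that the rule for fewer than 5 responders also covers the composites.
3. Reconcile SAP 7.5.5 (nominal p-values) with Protocol 8.4.2.3 (no testing). If p-values are kept for the composites, name the test; if not, exclude the composites from the SAP sentence. List the change in SAP 10.
4. The SAP amendment history shows that short-term reporting was under way before Version 3, so mark the Week 52 estimate as specified after the short-term unblinding.

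The cost is a few sentences and a small extension of a model the plan already uses. No new data, visits or subjects are needed, and the endpoints stay exploratory.
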